- Eos-FeNO Quadrant (0.15-20) 3 (L-H): Baseline blood eosinophil level <0.15 Giga/L and Baseline FeNO ≥ 20 ppb
- Eos-FeNO Quadrant (0.15-20) 4 (L-L): Baseline blood eosinophil level <0.15 Giga/L and Baseline FeNO <20 ppb
- Eos-FeNO Quadrant (0.3-20) 1 (H-H): Baseline blood eosinophil level ≥ 0.3 Giga/L and Baseline FeNO ≥ 20 ppb
- Eos-FeNO Quadrant (0.3-20) 2 (H-L): Baseline blood eosinophil level ≥ 0.3 Giga/L and Baseline FeNO <20 ppb
- Eos-FeNO Quadrant (0.3-20) 3 (L-H): Baseline blood eosinophil level <0.3 Giga/L and Baseline FeNO ≥ 20 ppb
- Eos-FeNO Quadrant (0.3-20) 4 (L-L): Baseline blood eosinophil level <0.3 Giga/L and Baseline FeNO <20 ppb
- Background controller type at randomization (ICS only, ICS + LABA)
- Baseline predicted FEV1% ($<80\%$, $\geq 80\%$)
- Baseline predicted FEV1% ($<$ median, \geq median)
- Baseline ACQ-7-IA (≤ 2 , >2)
- Baseline weight (≤ 30 , >30 kg)
- Atopic medical condition (Yes, No)
- Baseline Total IgE ($<$ median, \geq median)
- Baseline Total IgE (<100 IU/mL, ≥ 100 IU/mL)
- Age at onset of asthma (0 - <2 , 2 - <6 , ≥ 6)
- Number of severe asthma exacerbation prior to the study as defined in [Section 2.1.1](#) (≤ 1 , $=2$, >2)

Additional EOS-FeNO Quadrant analysis will be performed using alternative cut-off value for the baseline FeNO:

- Eos-FeNO Quadrant (0.15-35) 1 (H-H): Baseline blood eosinophil level ≥ 0.15 Giga/L and Baseline FeNO ≥ 35 ppb
- Eos-FeNO Quadrant (0.15-35) 2 (H-L): Baseline blood eosinophil level ≥ 0.15 Giga/L and Baseline FeNO <35 ppb

- Eos-FeNO Quadrant (0.15-35) 3 (L-H): Baseline blood eosinophil level <0.15 Giga/L and Baseline FeNO \geq 35 ppb
- Eos-FeNO Quadrant (0.15-35) 4 (L-L): Baseline blood eosinophil level <0.15 Giga/L and Baseline FeNO <35 ppb

A patient is considered to have ongoing atopic medical condition if he/she has any of the following: atopic dermatitis, allergic conjunctivitis or rhinitis, eosinophilic esophagitis, food allergy, hives; or has baseline serum total IgE \geq 100 IU/mL and at least one positive aeroantigen specific IgE (\geq 0.35 IU/mL) at baseline.

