The aforementioned subgroup analyses (except for the baseline eosinophil levels and baseline FeNO levels) will be performed in the Type 2 inflammatory asthma phenotype population and baseline blood eosinophils \geq 0.3 Giga/L population; and, the subgroup analyses concerning the baseline blood eosinophil level and baseline FeNO level will be performed in the full ITT population. The annualized rate of severe exacerbation events as defined in [Section 2.1.3.1](#) will be analyzed using a negative binomial regression model.

When performing the subgroup analysis in the Type 2 inflammatory asthma phenotype population or the full ITT population, the model will include the total number of events that occur during the observation period defined above as the response variable, with the treatment arm, age, baseline weight (\leq 30kg, >30kg), region, baseline blood eosinophil level (<0.3 Giga/L, \geq 0.3 Giga/L), baseline FeNO level (<20 ppb, \geq 20 ppb), baseline ICS dose level (medium/high) and number of severe exacerbation events within 1 year prior to the study as covariates. When performing the subgroup analysis in the baseline blood eosinophils \geq 0.3 Giga/L population, the baseline eosinophil level will be removed from the model covariates. Furthermore, in the Type 2 inflammatory asthma phenotype, baseline blood eosinophils \geq 0.3 Giga/L, or full ITT population, when performing the subgroup analysis that is defined by age, baseline weight, region, baseline blood eosinophil level, baseline FeNO level, baseline ICS dose level, or number of severe exacerbation events within 1 year prior to the study, the covariate that defines the subgroup will be removed from the model covariates.

[figure not shown]
Treatment groups, baseline weight, region, baseline eosinophil level, baseline FeNO level, and baseline ICS dose level will be treated as categorical variables. Age and number of severe exacerbation events within 1 year prior to the study will be treated as continuous variables. Log transformed observation duration will be the offset variable. In the case where the negative binomial regression model may not converge, a categorical variable for the number of severe exacerbation events within 1 year prior to study (1, 2, more than 2) will replace the corresponding continuous variable in the model.

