2.4.4.2 Analyses of key secondary efficacy endpoints

Statistical analysis methods for the key secondary endpoints are presented below.

2.4.4.2.1 Change from baseline in percentage predicted pre-bronchodilator (pre-BD) FEV₁ at Week 12

Primary statistical model and adjustment for covariates

The analysis of change from baseline in % predicted pre-BD FEV₁ at Week 12 is to assess the efficacy of dupilumab regardless of treatment adherence. The absolute change from baseline in % predicted FEV₁ at Week 12 will be analyzed using a mixed-effect model with repeated measures (MMRM) approach. The analysis for change from baseline in % predicted pre-BD FEV₁ will be performed in the Type 2 inflammatory asthma phenotype, baseline blood eosinophils ≥ 0.3 Giga/L, baseline blood eosinophils ≥ 0.15 Giga/L, baseline FeNO ≥ 20 ppb and full ITT populations.

When performing the key secondary endpoint analysis in the Type 2 inflammatory asthma phenotype, baseline blood eosinophils ≥ 0.15 Giga/L, and full ITT populations, the model will include change from baseline in % predicted FEV₁ values up to Week 12 as response variables, and treatment, baseline weight, region, ethnicity, baseline eosinophil level, baseline FeNO level, baseline ICS dose level, visit, treatment by-visit interaction, baseline % predicted FEV₁ value and baseline-by-visit interaction as covariates. When performing the key secondary endpoint analysis in the baseline blood eosinophils ≥ 0.3 Giga/L population, the baseline eosinophil level will be removed from the model covariates. When performing the key secondary endpoint analysis in the baseline FeNO ≥ 20 ppb population, the baseline FeNO level will be removed from the model covariates.

Treatment group, baseline weight, region, baseline eosinophil level, baseline FeNO level, ethnicity, baseline ICS dose level, and visit will be treated as categorical variables. For patients who discontinue the treatment before Week 12, they will be asked and encouraged to return to the clinic for all remaining study visit and the additional off-treatment % predicted FEV₁ values measured up to Week 12 will be included in the primary analysis. For patients who withdraw from the study before Week 12, % predicted FEV₁ values will be missing after study discontinuation. No imputation will be performed for missing values in the primary analysis. This estimand

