compares the change from baseline in % predicted pre-BD FEV1 for the patients randomized to the dupilumab and placebo arms, regardless of what treatment patients actually received. It assesses the benefits of the treatment policy or strategy relative to placebo.

An unstructured correlation matrix will be used to model the within-patient errors. Parameters will be estimated using restricted maximum likelihood method with the Newton-Raphson algorithm. Statistical inferences on treatment comparisons for the change from baseline in % predicted FEV1 at Week 12 will be derived from the mixed-effect model. Difference in LS mean change from baseline, the corresponding 95% CI and the p-value with Kenward-Roger adjustment will be provided for comparison for dupilumab against placebo. In addition, descriptive statistics including number of patients, mean, standard error and LS mean of change from baseline will be provided.

A sample SAS code can be found below:

```
proc mixed data=adsd.adre method=reml;

    where paramcd='FEV1PP' and ATPT='PRE-BRONCHODILATOR' and avisitn ge 3 and
    avisitn le 8 and ittfl='Y';

    class subjid weight eosblgpn1 fenoblgn1 ics trt01pn avisitn cntygr1n ethnicity;

    model chg = trt01pn weight ics eosblgpn1 fenoblgn1 cntygr1n ethnicity avisitn
    trt01pn*avisitn base base*avisitn/ddfm=kr residual;

    repeated avisitn/type=un subject=subjid;

    lsmeans trt01pn*avisitn /pdiff cl;

    estimate 'dupilumab vs Placebo at Week 12 Visit 8'

    trt01pn -1 1 trt01pn*avisitn 0 0 0 0 0 -1 0 0 0 0 0 1/cl;

run;
```

The primary estimand for the key secondary endpoint is summarized as in below [Table 7](#).

Table 7 - Summary of primary estimand for key secondary endpoint

Endpoint Category (estimand)	Estimands			
	Endpoint	Population	Intercurrent event(s) strategy and missing data handling	Population-level summary
Primary objective: The primary objective is to evaluate the efficacy of dupilumab in children 6 to <12 years of age with uncontrolled persistent asthma				

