First, missing values will be imputed by PMM-MI as illustrated above. The imputed values in placebo group will then be shifted by adding a sequence of positive values and the imputed values in dupilumab group will be shifted by subtracting a sequence of positive values. For each combination of the shift parameters, each of the imputed and shifted datasets will be analyzed with the ANCOVA model and their results will be combined using Rubin's formula to generate statistical inference. LS mean difference between dupilumab and placebo in change from baseline in % predicted pre-BD FEV1 at Week 12 and the corresponding p-values will be provided for each combination of shift parameters.

The missing data sensitivity analyses for the key secondary endpoint analysis will be performed in the Type 2 inflammatory asthma phenotype and baseline blood eosinophils ≥ 0.3 Giga/L populations. When performing the sensitivity analyses in the population with Type 2 inflammatory asthma phenotype, the model will include treatment, baseline weight, region, ethnicity, baseline eosinophil level, baseline FeNO level, baseline ICS dose level, visit, treatment by-visit interaction, baseline % predicted FEV1 value and baseline-by-visit interaction as covariates. When performing the sensitivity analyses in the population with baseline blood eosinophils ≥ 0.3 Giga/L, the baseline eosinophil level will be removed from the model covariates.

More details of the imputation and analyses methods are included in [Appendix D](#).

Subgroup analysis

To assess the consistency of treatment effects across the subgroup levels, subgroup analyses will be conducted for the change from baseline in % predicted pre-BD FEV1 at Week 12 in the same set of subgroups as defined for the primary endpoint of annualized rate of severe exacerbation events. The subgroup analyses (except for the baseline eosinophil levels and baseline FeNO levels) will be performed in the Type 2 inflammatory asthma phenotype population and baseline blood eosinophils ≥ 0.3 Giga/L population; and, the subgroup analyses for the baseline blood eosinophil level and baseline FeNO level will be performed in the full ITT population. The same MMRM model for the key secondary endpoint will be applied for the subgroup analyses.

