When performing the subgroup analysis in the Type 2 inflammatory asthma phenotype population or the full ITT population, the model will include change from baseline in % predicted FEV1 values up to Week 12 as response variables, and treatment, baseline weight, region, ethnicity, baseline eosinophil level, baseline FeNO level, baseline ICS dose level, visit, treatment by-visit interaction, baseline % predicted FEV1 value and baseline-by-visit interaction as covariates. When performing the subgroup analysis in the baseline blood eosinophils ≥ 0.3 Giga/L population, the baseline eosinophil level will be removed from the model covariates. Furthermore, in the Type 2 inflammatory asthma phenotype, baseline blood eosinophils ≥ 0.3 Giga/L, or full ITT population, when performing the subgroup analysis that is defined by age, baseline weight, region, gender, baseline blood eosinophil level, baseline FeNO level, baseline ICS dose level, or baseline % predicted FEV1, the covariate that defines the subgroup will be removed from the model covariates.

Treatment-by-subgroup interaction at Week 12 and its p-value will be derived from an MMRM model. If quantitative treatment by subgroup interaction at Week 12 is detected with nominal p-value <0.05 for any subgroup factor, the Gail-Simon test will be used to test the qualitative interaction. Summary statistics of change from baseline in % predicted pre-bronchodilator FEV1 will be provided within each subgroup. Forest plot of LS mean difference and corresponding CIs comparing dupilumab vs placebo for the subgroups will be provided.

Distribution of change from baseline in percent predicted pre-BD FEV1

Water fall plots of change from baseline in % predicted FEV1 at Week 12 and Week 52 will be presented in the Type 2 inflammatory asthma phenotype population and baseline blood eosinophils ≥ 0.3 Giga/L population.

Treatment-by-Type 2 biomarker interaction

To examine the ability of FeNO to predict the treatment effect of dupilumab independent of blood eosinophil levels for the key secondary endpoint, the treatment-by-biomarker interactions will be tested with MMRM model, which includes change from baseline in % predicted FEV1 values up to Week 12 as response variables, and with the following different sets of model covariates, respectively. A threshold value of 0.15 will be utilized for the nominal p value of interaction test.

Biomarker covariate and treatment -by-biomarker interaction	Model covariates

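### The SAP's subgroup rule drops the continuous baseline % predicted FEV1 from subgroups that are only two-way cuts of it, at a modest cost in precision

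*SAP*

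**What the plan says.** SAP 2.4.4.2.1 runs the key secondary MMRM "in the same set of subgroups as defined for the primary endpoint". The covariate list for those subgroup models ends with "baseline % predicted FEV1 value and baseline-by-visit interaction as covariates". A removal rule follows. It lists several subgroup definers and closes with "baseline ICS dose level, or baseline % predicted FEV1, the covariate that defines the subgroup will be removed from the model covariates".

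Other places settle what this means:

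- **The subgroups.** The list in SAP 2.4.4.1 has two entries labelled "Baseline predicted FEV1" as a percentage, one split at 80% and one at the median.
- **The covariate.** The sentence naming the categorical terms of the MMRM ends "baseline ICS dose level, and visit will be treated as categorical variables" and does not include the baseline value. In the sample code the CLASS line is "class subjid weight eosblgpn1 fenoblgn1 ics trt01pn avisitn cntygr1n ethnicity". The baseline variable appears only in the MODEL line, as "trt01pn*avisitn base base*avisitn/ddfm=kr residual". It is therefore continuous.
- **The parallel rule.** For exacerbations, SAP 2.4.4.1 has the same rule, whose list ends "or number of severe exacerbation events within 1 year prior to the study, the covariate that defines the subgroup will be removed".

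Protocol 11.4.2.2.6 plans the key secondary subgroup analyses but contains no removal rule, so the rule comes from the SAP. Nothing elsewhere puts the continuous baseline back for these subgroups.

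**The concern.** Dropping the covariate that defines a subgroup makes sense when it takes one value there. Region, ICS level and weight group are constant within their own levels and carry no information. A continuous variable cut in two is different: within each part it still varies, and here it is the outcome's own baseline. The SAP keeps that baseline in the main MMRM, in the missing-data ANCOVA models and in the biomarker-interaction models. These subgroups are the exception, and no reason is given.

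The subgroup estimates and forest plots are there to show whether the Week 12 effect is consistent across baseline lung function. FEV1 is not a stratification factor (SAP 1.1), so the arms can differ by chance in baseline FEV1 within a part. Without the covariate, that difference stays in the estimate.

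The parallel rule raises two smaller points. The number of prior exacerbations is continuous in the exacerbation model and still varies in the subgroup with more than two. And it is unclear whether the 0.3 Giga/L eosinophil term stays in the subgroup at or above 0.15 Giga/L.

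**Working it through.** The plan states no figure to reproduce here. The check is of the model terms first, then of the size of the loss.

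**1. Does removal lose the adjustment?** The model has two baseline terms, the value and its interaction with visit. The rule speaks of the covariate and is silent on the interaction. There are six post-baseline visits up to Week 12 (Weeks 2, 4, 6, 8, 10, 12). With visit as a class variable, visit plus baseline-by-visit gives a design of rank 12. Adding the baseline main effect also gives rank 12. So if the interaction stays, the fit equals the fully adjusted model; adjustment is lost only if both terms go.

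**2. Size if both go.** Inputs:

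- 2:1 allocation and about 345 children in the Type 2 population (SAP 1.1).
- Assumed, because the documents give neither: equal SDs at baseline and Week 12 (set to 1), a normal baseline, and correlation ρ from 0.4 to 0.8.

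Write X for baseline and Y for Week 12. Then Y − X = −(1 − ρ)X + e, with var(e) = 1 − ρ². Within one half of a median split, var(X) = 1 − 2/π = 0.363.

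- With the baseline covariate: variance 1 − ρ².
- Without it: (1 − ρ²) + 0.363(1 − ρ)².
- Ratio: 1 + 0.363(1 − ρ)/(1 + ρ).

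| ρ | (1 − ρ)/(1 + ρ) | Variance ratio | SE ratio |
|---|---|---|---|
| 0.4 | 0.429 | 1.156 | 1.075 |
| 0.5 | 0.333 | 1.121 | 1.059 |
| 0.6 | 0.250 | 1.091 | 1.044 |
| 0.7 | 0.176 | 1.064 | 1.032 |
| 0.8 | 0.111 | 1.040 | 1.020 |

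**3. Simulation check.** 4,000 trials of 345 children at 2:1, analysing the below-median half, with a true effect of 0.3 SD. The variance ratio was 1.11 at ρ = 0.5 and 1.04 at ρ = 0.7. These are slightly below the formula, which does not charge for estimating the slope; simulation error also contributes. Mean estimates without and with the covariate were 0.306 and 0.304 at ρ = 0.5, and 0.294 and 0.294 at ρ = 0.7. There is no bias on average.

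**4. Where the extra variance comes from.** A half of 345 is 172.5 children, 115 against 57.5. The SD of the chance baseline difference is √0.363 × √(1/115 + 1/57.5) = 0.097 baseline SDs. It enters the estimate multiplied by −(1 − ρ). A one-SD chance imbalance therefore moves the estimate by √(variance ratio − 1) adjusted standard errors: √0.156 = 0.395 at ρ = 0.4, and √0.040 = 0.20 at ρ = 0.8. The square of that shift is exactly the excess variance in step 2. Lost precision and uncorrected imbalance are one cost, not two.

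**5. The 80% cut.** The loss depends on where 80% falls in the baseline distribution, which is not given. If the baseline had mean 78 and SD 14 (assumed) and ρ = 0.5, keeping the covariate would cut the variance by 11.7% below 80% and 10.0% at or above it. The increase from dropping it is 1/(1 − 0.117) − 1 = 13% and 1/(1 − 0.100) − 1 = 11%, the same order as the median split.

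**The case against.** The case against has real force on five points.

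- **The text does not say that baseline-by-visit is dropped.** If it stays, nothing is lost. This stands as a condition. Dropping an interaction with its main effect is the ordinary reading, but a plan that allows two different fits should say which is meant.
- **Regression to the mean is no threat to the comparison.** A reader might infer that cutting on baseline and then leaving it out biases the effect. Both randomised arms regress alike, and the simulation shows no average bias. The loss is also smaller within a half than in an unsplit population: at ρ = 0.5 the ratio there is 2/(1 + ρ) = 1.33, against 1.12 in a half.
- **The analysis is not wholly unadjusted.** The response is still change from baseline, and weight, region, ethnicity, eosinophil, FeNO and ICS level remain in the model. Only the baseline covariate is missing.
- **These results are supportive.** No subgroup cut on FEV1 appears in SAP Table 9 or Table 10, and none is powered. The interaction p-value comes from a separate MMRM whose covariates the SAP does not list.
- **The eosinophil point depends on reading.** A reader might infer that the same children will certainly get two rate ratios. The model term is a split at 0.3 Giga/L, which arguably does not define a subgroup cut at 0.15, so keeping it is an equally available reading.

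What survives is that the rule names a continuous covariate for removal where it is not constant, without stated reason.

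**Conclusion.** The point holds, at modest size. On the natural reading, the Week 12 FEV1 effect in the subgroups cut on baseline FEV1 is estimated without the outcome's own baseline. For a median split this costs about 4% to 16% in variance over correlations of 0.8 to 0.4. It rests on those assumed correlations, on equal SDs and a normal baseline, on no allowance for the other covariates, and on baseline-by-visit being removed too.

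A reader might go further and conclude that the key secondary result or type I error control is compromised. The documents do not support that: the main MMRM keeps the baseline value and its visit interaction, and the rule touches subgroup models only.

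On the parallel rule, the prior-exacerbation count does vary in the subgroup with more than two, unless the SAP's categorical fallback for non-convergence is in use, in which case it is constant there. The eosinophil wording is ambiguous. On one reading the 0.3 term is dropped in the full ITT subgroup at or above 0.15 Giga/L. Those are by definition the same children as the population tested 2nd in both hierarchies, whose model keeps the term, so the two results would differ.

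**What to change.** In SAP 2.4.4.2.1 and 2.4.4.1, replace the removal sentence with a rule that a covariate is removed only when it is constant within the subgroup level. Then state that:

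- continuous baseline % predicted FEV1 and its visit interaction stay in the FEV1 model for the 80% and median subgroups;
- the continuous prior-exacerbation count stays in the exacerbation model for the subgroup with more than two events;
- the 0.3 Giga/L eosinophil term stays in the subgroup at or above 0.15 Giga/L, so that it matches the population analysis of the same children.

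Two tidying edits fit in the same place. The 2.4.4.2.1 rule also names age and gender, which are not covariates in that model. And the covariates of the FEV1 treatment-by-subgroup interaction model should be listed, as they are for exacerbations in 2.4.4.1.

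The cost is a few sentences in the SAP. No new data are needed, the retained terms are already collected and derived, and there is no material downside.

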2.4.4.3 Analyses of secondary efficacy endpoints

2.4.4.3.1 Change from baseline for continuous endpoints

Change from baseline in ACQ-7-IA Week 24 will be analyzed using MMRM model including change from baseline up to Week 24 as response variables, regardless if the patient is on treatment or not when the endpoint is measured. Change from baseline in FeNO at Week 12 will be analyzed using MMRM including change from baseline up to Week 12 as response variables, regardless if the patient is on treatment or not when the endpoint is measured. The analyses for the secondary endpoints of ACQ-7-IA and FeNO will be performed in the Type 2 inflammatory

asthma phenotype, baseline blood eosinophils ≥ 0.3 Giga/L, baseline blood eosinophils ≥ 0.15 Giga/L, baseline FeNO ≥ 20 ppb and full ITT populations. When performing these analyses in the Type 2 inflammatory asthma phenotype, baseline blood eosinophils ≥ 0.15 Giga/L or full ITT population, the MMRM models will include treatment, age, baseline weight, region (pooled country), baseline eosinophil level, baseline FeNO level, baseline ICS dose level, visit, treatment by-visit interaction, baseline endpoint value, and baseline-by-visit interaction as covariates. When performing these analyses in the baseline blood eosinophils ≥ 0.3 Giga/L population, the baseline eosinophil level will be removed from the model covariates. When performing these analyses in the baseline FeNO ≥ 20 ppb population, the baseline FeNO level will be removed from the model covariates. An MMRM model including measurements up to Week 52 will also be used to derive LS mean change at all time-points in the Type 2 inflammatory asthma phenotype and baseline blood eosinophils ≥ 0.3 Giga/L populations, with including the same set of model covariates as specified for the secondary endpoint analyses. Differences in LS means, the corresponding 95% CI and the p-value will be provided for comparison between dupilumab and placebo along with descriptive statistics.

In the Type 2 inflammatory asthma phenotype and baseline blood eosinophils ≥ 0.3 Giga/L populations, change from baseline for other continuous endpoints at all time-points will be analyzed using MMRM model including measurements up to Week 52. The model will include change from baseline of these endpoints from all available planned time points up to Week 52 as response variables, regardless if the patient is on treatment or not when the endpoint is measured. When performing these analyses in the Type 2 inflammatory asthma phenotype population, treatment, age, baseline weight, region (pooled country), baseline eosinophil level, baseline FeNO level, baseline ICS dose level, visit, treatment by-visit interaction, baseline endpoint value and baseline-by-visit interaction will be the model covariates. When performing these analyses in the baseline blood eosinophils ≥ 0.3 Giga/L population, the baseline eosinophil level will be removed from the model covariates. Ethnicity will be included as the covariate only in the models for spirometry parameters, specifically. Differences in LS means, the corresponding 95% CI and the p-value will be provided for comparison between dupilumab and placebo along with descriptive statistics.

In addition to the MMRM analyses for change from baseline in ACQ-7, ACQ-5, and AQLQ total score a responder analysis will also be performed for these endpoints at Week 12, 24, 36 and 52, in the Type 2 inflammatory asthma phenotype and baseline blood eosinophils ≥ 0.3 Giga/L populations. For ACQ-7 score, a logistic regression model will be used to compare percentage of patients who reached MCID (responders) in dupilumab and placebo group at the time points aforementioned correspondingly. Patients with change from baseline in ACQ-7 ≤ -0.5 will be considered as responders. Patients with change from baseline in ACQ-7 > -0.5 or with missing value will be considered as non-responders. When performing the analyses in the Type 2 inflammatory asthma phenotype population, the logistic model will include treatment, age, baseline weight, region (pooled country), baseline eosinophil level, baseline FeNO level, baseline ICS dose level, and baseline ACQ-7 score as covariates. When performing the analyses in the baseline blood eosinophils ≥ 0.3 Giga/L population, the baseline eosinophil level will be removed from the model covariates. Odds ratio of being a responder comparing dupilumab and placebo group will be provided along with the corresponding 95% CI and p-value. Descriptive statistics

including number and percentage of responders will also be provided. Responder analysis for ACQ-5 and AQLQ global score will be performed in the same way. For ACQ-5, a patient is considered as a responder if change from baseline in ACQ-5 score ≤ -0.5 , or as a nonresponder if change from baseline in ACQ-5 score > -0.5 or missing. For AQLQ global score, a patient is considered as a responder if change from baseline in AQLQ global score ≥ 0.5 , or as a non-responder if change from baseline < 0.5 or missing.

